4.7.2 Imatinib

Imatinib should be taken with a meal and a large glass of water. Imatinib tablets should not be crushed. Direct contact of crushed tablets with the skin or mucous membranes should be avoided. If such contact occurs, wash thoroughly as outlined in the package insert.

If a dose is missed, patients should be advised to take their dose as soon as possible unless it is almost time for their next dose in which case the missed dose should not be taken. A double dose should not be taken to make up for any missed dose.

Imatinib can be dissolved in water or apple juice for patients having difficulty swallowing. The required number of tablets should be placed in the appropriate volume of beverage (approximatel 50 mL for a 100 mg tablet and 200 mL for a 400 mg tablet) and stirred with a spoon. The suspension should be administered immediately afer complete disintegration of the tablet(s).

Tablets come in 100 mg very dark yellow to brownish orange, film-coated tablets, round, biconvex with bevelled edges as well as 400 mg tablets with very dark yellow to brownish orange, film-coated tablets, ovaloid, biconvex with bevelled edges.

Imatinib should be stored at 25°C (77°F). Excursions permitted to 15°C to 30°C (59°F to 86°F). Protect from moisture. Dispense in a tight container.

Procedures for the proper handling and disposal of anticancer drugs should be considered.

4.7.3 Ruxolitinib

Ruxolitinib is dose orally and can be administered with or without food.

If a dose is missed, the patient should not take an additional dose, but should take the next usual prescribed dose.

Ruxolitinib phosphate is a kinase inhibitor. It is a white to off-white to light pink powder and is soluble in aqueous buffers across a pH range of 1 to 8.

Each ruxolitinib tablet contains ruxolitinib phosphate equivalent to 5 mg, 10 mg, 15 mg, 20 mg, and 25 mg of ruxolitinib free base together with microcrystalline cellulose, lactose monohydrate, magnesium stearate, colloidal silicon dioxide, sodium starch glycolate, povidone and hydroxypropyl cellulose.

Dosage Forms and Strengths

5 mg tablets – round and white with "INCY" on one side and "5" on the other 10 mg tablets – round and white with "INCY" on one side and "10" on the other 15 mg tablets – oval and white with "INCY" on one side and "15" on the other 20 mg tablets – capsule-shaped and white with "INCY" on one side and "20" on the other 25 mg tablets – oval and white with "INCY" on one side and "20" on the other

Ruxolitinib should be stored at room temperature 20°C to 25°C (68°F to 77°F); excursions permitted between 15°C and 30°C (59°F and 86°F).

4.8 Pharmacology Assessments

Serum concentration and pharmacokinetic (PK) parameters of OncoTreat-prioritized agents undergoing trial in subjects with advanced pancreatic cancer are going to be measured in the Clinical Pharmacology and Toxicology Laboratory (CPTL), Department of Pathology and Cell Biology, Columbia University Irving Medical Center (CUIMC). CPTL is a New York State CLIA-certified lab dedicated mostly to assay development for drugs in different biological specimens using advanced technology such as ultra-performance liquid chromatography tandem mass spectrometry (LC-MS/MS). In support of OncoTreat, CPTL is going to develop and offer assays for those FDA-approved drugs as well as investigational agents that are prescribed based on this methology. Assays will be developed using LC-MS/MS and target ranges for the Therapeutic Drug Monitoring (TDM) of these various compounds will be derived from the literature. The CPTL has already developed an LC-MS/MS method for the simultaneous quantification of capecitabine, imatinib, and ruxolitinib (see complete details of methods in Appendix 17.5):

	Le monto assay method over v	
	MRM	RT, min
Imatinib	494.121>217.019*	2.31
	494.121>934.045	

Table 1: LC-IVIS/IVIS assay method overview	Table 1:	LC-MS/MS	assay	method	overview
---	----------	----------	-------	--------	----------

IS: 13CD3-	498.195>394.091*	2.31							
Imatinib	498.195>221.044								
Ruxolitinib	307.127>186.228	2.65							
	307.127>131.73								
IS: Ruxolitinib-	316.133>186.228	2.61							
D9	316.133>131.73								
Capecitabine	360.181>244.036	2.96							
	360.181>173.994								
IS: Ruxolitinib-	316.133>186.228	2.61							
D9	316.133>131.73								
*Transition used for quantification									

4.8.1 Capecitabine

Capecitabine is the oncology pro-drug of 5-fluorouracil (5FU). Capecitabine is administered orally and undergoes mainly hepatic metabolism where it is first biotransformed into 5'-deoxy-5-fluorocytidine (5'-DFCR) by carboxylesterases and subsequently to 5'-deoxy-5-fluorouridine (5'-DFUR) by cytidine deaminase. Metabolism of capecitabine involves different enxymes, where thymidine phosphorylase converts 5'-DFUR to the active drug 5FU [71].

Concentration levels of capecitabine and both 5'-DFCR and 5'-DFUR are measured in PK studies [72]. Several PK studies were assessed previously in serum for capecitabine, where t_{max} ranged from 0.5 to 2 hours, with a C_{max} of 5000-9500 ng/mL and $t_{1/2}$ of 34-50 min. After the administration of a standard dose of capecitabine, it might be expected serum concentrations within 5-10,000 ng/mL.

Dosage: Capecitabine 1000 mg/m² given orally twice daily, separated 12 hours apart, on Days 1-14 of a 21-day cycle, to be taken with water within 30 minutes after a meal.

Sampling: Based on a 21-day cycle, as mentioned above, peak levels will be measured 2 hours after administration of capecitabine on day 1 and cycle 1 day 8.

Sample Handling: Peripheral blood will be collected in a tube containing 500 nM tetrahydrouridine (THU) to avoid *ex vivo* conversion of 5'-DFCR to 5'-DFUR [73] and will be allowed to clot for 30-60 min followed by centrifugation at 3000 rpm, 4°C, for 10 min.

Sample Storage: Serum samples will be stored at -80°C.

Extraction: Capecitabine will be extracted from the serum samples using the above mentioned protein precipitation extraction procedure. Minimum volume of blood sample considering duplicates for TDM (and PK) studies should be no less than 300 μ L (120 μ L is needed for one extraction).

Quantification: Concentration of capecitabine will be measured by a New York State Department of Health (and thereby CLIA-) approved LC-MS/MS assay developed for the

simultaneous quantification of OncoTreat-prioritized drugs. The method is based on an existing New York State DOH-approved assay for imatinib developed by CPTL for its clinical services, with only minor modifications.

Target Range: The target ranges for peak levels will be 5,000 - 10,000 ng/mL for capecitabine in serum.

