2.2 Secondary Objectives & Endpoints

*Note: The secondary objects only apply for patients who are initiated on treatment with an OncoTreat-prioritized FDA-approved or early-phase investigational drug.

2.2.1 Objectives:

The secondary objectives of this study are to:

- To describe the safety and tolerability of using OncoTreat to inform rational treatment decision in subjects with advanced PDA who have progressed on one or two prior lines of therapy.
- To assess the efficacy of OncoTreat by estimating the disease control rate (DCR) at 16 and 24 weeks, the median progression-free survival (PFS), the overall survival (OS), and the CA 19-9 tumor marker response.
- To assess the pharmacokinetics of each OncoTreat-prioritized agent in subjects with advanced PDA.

2.2.2 Endpoints:

Secondary endpoints of interest include:

- Safety/tolerability
 - Incidence of Grade 3/4 adverse events (AEs) in terms categorized and graded according to the National Cancer Institute Terminology Criteria for Adverse Events (NCI CTCAE v4.0).
 - Incidence of dose modifications, interruptions, and discontinuations.
 - Note: OncoTreat-prioritized agents will be dosed at the FDA-approved dose (if available) or the recommended phase 2 dose for investigational agents. Safety endpoints as they pertain to specific drugs will not be assessed in this prospective study, as only a very small number of patients will be assigned to any one of these drugs, all of which are FDAapproved or have been studied in early phase clinical trials and have track records of safety/tolerability.
- DCR, defined as the proportion of subjects with a complete or a partial response as the best response or stable disease, according to RECIST v1.1 criteria.
- PFS, defined as the time from first dose of OncoTreat-prioritized drug to the first occurrence of disease progression or death from any cause (whichever occurs first), using RECIST v1.1 criteria.
- OS, defined as the time from first dose of OncoTreat-informed study drug to death due to any cause.
- Tumor marker response of CA 19-9, defined as ≥ 50% in CA 19-9 in relation to the baseline level at least once during the treatment period.
- Serum concentration or PK parameters for each OncoTreat-prioritized agent.
- Relationship between serum concentration or PK parameters and endpoints of interest.

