Capecitabine has almost 100% oral bioavailability and exhibits linear increases in C_{max} and AUC with dosage increases [45]. After 2 doses of 1250 mg/m², the drug undergoes rapid absorption, with peak plasma levels of 3.9 mg/L achieved in 1.5 to 2 hours. In comparison, C_{max} for the active metabolite FU was lower at 0.66 mg/L with a similar T_{max} of 2 hours. AUC values for the parent drug and active metabolite for the same dosage were 5.96 mg and 1.34 mg h/L, respectively. In a study of 34 patients undergoing 14 continuous days of capecitabine therapy at daily doses ranging from 502 to 3514 mg/m², no significant accumulation of capecitabine or its metabolites was seen [45, 46].

A crossover study evaluated the effect of food on capecitabine pharmacokinetics in 11 patients with colorectal cancer [47]. Doses of 666 or 1255 mg/m² give twice daily were administered either after an overnight fast or within 30 minutes of finishing a standard breakfast on days 1 and 8. The AUC of capecitabine decreased in the presence of food but the AUC of the cytotoxic drug FU was only minimally affected. Dosing with food is still recommended, as this was how the drug was dosed in clinical trials and because the reported response rate and toxicity profiles reflect the administration of capecitabine within 30 minutes of finishing a meal.

The predominant route of elimination is renal. The use of capecitabine in patients with renal impairment was compared in 24 patients with various solid tumors [48]. Capecitabine was dosed orally at 1250 mg/m2 twice daily for 2 weeks followed by a 1-week rest period. All 4 patients with severe renal dysfunction (defined as CrCl <30 mL/min) experienced serious grade 3 or 4 adverse effects. From these results, it is recommended that patients with CrCl 30 to 50 mL/min receive 75% of the recommended starting dose of capecitabine and that use of this agent be avoided in patients with CrCl <30 mL/min because of the potentially increased risk of adverse events.

No dosing adjustments for patients with hepatic dysfunction are recommended with capecitabine.

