9.4.4 Eastern Cooperative Oncology Group (ECOG) Performance Status

The investigator or qualified designee will assess ECOG status (Appendix A) at screening, prior to the administration of each dose of trial treatment, and at discontinuation of trial treatment as specified in the Trial Flow Chart (Section 9).

9.4.5 Tumor Imaging and Assessment of Disease

CT chest, abdomen, and pelvis with contrast will be performed at baseline screening, prior to the administration of study drugs, and every 8 weeks thereafter. Subjects will be evaluated for diease response and progression according to RECIST v1.1. Disease status categories include complete response (CR), partial response (PR), stable disease (SD), and progression of disease (PD).

9.4.6 Tumor Tissue Collection, Pharmacokinetics, & Correlative Studies Blood Sampling All patients will have tumor biopsy specimens obtained at baseline prior to study drug administration and then at week 4 (optional) to assess for successful collapse of the master regulator signature in a given patient's tumor. A biopsy will also be requested (optional) at the time of disease progression. Tissue collection, handling, processing, and storage instructions are described in the separate study manual.

Peripheral blood will be collected for pharmacokinetic analysis only during Cycle 1. The timing of blood sampling will vary by study drug (Section 4.8). The exact times of medication administration and the times of these blood samples must be recorded on the appropriate CRF. A validated assay will be used to measure plasma drug concentration. Blood processing, handling, and storage instructions are described in Section 4.8 as well as in the separate study manual.

Peripheral blood will be collected pre-treatment, cycle 1 day 1, and cycle 2 for future evaluation of biomarkers. The analyses may include genomics, transcriptomics, and proteomics. Assessment of ctDNA and OncoTreat analysis on circulating tumor cells (CTCs) may also be performed.

9.4.7 Laboratory Procedures/Assessments

Details regarding specific laboratory procedures/assessments to be performed in this trial are provided below. Laboratory tests for hematology, chemistry, urinalysis, and others are specified in the Trial Flow Chart (Section 9).

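### Section 4.8.1 treats a single 2-hour capecitabine sample as the peak and sets a C_max-based target for it, a pairing that on the plan's own figures tends to make adequate exposure look low

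*Combined protocol and SAP*

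**What the plan says.** Section 4.8.1 takes one capecitabine sample on each of two days in cycle 1: "peak levels will be measured 2 hours after administration of capecitabine on day 1 and cycle 1 day 8". The target is stated for the peak: "The target ranges for peak levels will be 5,000 - 10,000 ng/mL for capecitabine in serum". The same section summarises earlier serum studies, in which t_max "ranged from 0.5 to 2 hours, with a C_{max} of 5000-9500 ng/mL", with a half-life of 34-50 minutes. It gives no mg/m² dose for those studies. Section 4.8 says only that "target ranges for the Therapeutic Drug Monitoring (TDM) of these various compounds will be derived from the literature".

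Section 4.5.1 describes the same drug differently. After 1250 mg/m² it reports rapid absorption "with peak plasma levels of 3.9 mg/L achieved in 1.5 to 2 hours", and says that capecitabine "exhibits linear increases in C_{max} and AUC with dosage increases". The study dose is 1000 mg/m² twice daily (sections 4.3.1 and 4.8.1).

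The measurements have two uses. Section 2.2.2 lists as a secondary endpoint "Serum concentration or PK parameters for each OncoTreat-prioritized agent", and also the relation of these values to other endpoints. Section 4.1, item (8), allows the treating physician, after discussion with the investigator, to use PK results together with toxicity when changing the dosing schedule.

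**The concern.** A target built from C_max values is a fair yardstick only for a sample that captures C_max, in the same matrix and at a comparable dose. Here the sample is fixed at the latest end of the t_max range in 4.8.1, and the half-life is short. The other peak reported in the plan lies below the target floor at a dose higher than the one given in this study. Both features push the same way, towards reading adequate exposure as low.

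At stake are the interpretation of a secondary PK endpoint and its exposure-response reading, and a discretionary input to dosing, in the few patients who will receive capecitabine.

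**Working it through.** **Inputs.** From 4.8.1: sample at 2 h; target 5,000-10,000 ng/mL (serum); C_max 5,000-9,500 ng/mL (serum, dose not stated); t_max 0.5-2 h; half-life 34-50 min; study dose 1000 mg/m². From 4.5.1: plasma peak 3.9 mg/L at 1250 mg/m², at 1.5-2 h; C_max linear in dose.

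**Where the target comes from.** The 4.8.1 C_max range gives the lower limit exactly (5,000) and the upper limit after rounding up (9,500 to 10,000). The 4.5.1 peak gives neither limit.

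**Target against the 4.5.1 peak.** No PK model is needed.
- 3.9 mg/L × 1000 = 3,900 ng/mL. Shortfall from the floor: 1 - 3,900/5,000 = 22%.
- At the study dose, reading linear as proportional: 3,900 × 1000/1250 = 3,120 ng/mL. Shortfall: 1 - 3,120/5,000 = 37.6%, about 38%.
- Serum-to-plasma ratio needed to close the gap: 5,000/3,900 = 1.28 and 5,000/3,120 = 1.60. The documents give no such ratio.

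**The 2-hour value as a share of C_max.** The plan gives no concentration curve, so two are assumed.
- Curve A, decline at the stated half-life straight from the peak: share = 0.5^((120 - t_max)/t½), times in minutes.
- Curve B, one-compartment oral absorption without lag: k = ln 2/t½; ka solved from t_max = ln(ka/k)/(ka - k); share = C(120)/C(t_max).

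| t_max | Curve A (t½ 34 / 50 min) | Curve B (t½ 34 / 50 min) | Range |
|---|---|---|---|
| 0.5 h | 0.160 / 0.287 | 0.260 / 0.363 | 16-36% |
| 1 h | 0.294 / 0.435 | 0.741 / 0.740 | 29-74% |
| 1.5 h | 0.542 / 0.660 | 0.963 / 0.956 | 54-96% |
| 2 h | 1 / 1 | 1 / 1 | 100% |

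The width of the middle rows reflects the choice of curve. Curve A is the steep case, because it allows no absorption after the peak. Curve B is the mild case, and at late peaks it strains its own input: with t_max at 1.5 h it needs ka < k, which implies a terminal half-life of about 79-133 min against the stated 34-50. Neither curve should be quoted alone.

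**What the cited C_max range would read at 2 h, across both curves.**
- 0.5 h peak: 5,000 reads 798-1,816 and 9,500 reads 1,517-3,450. The whole range falls under the floor.
- 1 h peak: 5,000 reads 1,471-3,705 and 9,500 reads 2,796-7,040. The bottom falls under the floor; the top depends on the curve.
- 1.5 h peak: 5,000 reads 2,712-4,814 and 9,500 reads 5,154-9,147. The bottom falls under the floor; the top clears it.
- 2 h peak: the reading equals C_max and the whole range meets the floor.

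**The case against.** The target agrees with the C_max range in its own section, and that range is in serum, the matrix to be assayed. The competing 3,900 ng/mL is a plasma figure from a different source, with no spread given. Scaling it to 3,120 treats linear as strictly proportional. Two hours lies inside both stated t_max ranges, and under the 1.5-2 h of 4.5.1 the sample is taken at or shortly after the peak. The secondary endpoints can be analysed on the recorded concentration without any target range. Dose changes for capecitabine in Table 2 follow toxicity grade and, unlike imatinib and ruxolitinib, capecitabine has no escalation provision. Section 4.1(8) is permissive and pairs PK with toxicity.

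Most of this stands, and it limits the point. A reader might infer that the target is wrong, that most capecitabine patients will be classed as under-exposed, or that doses will be raised as a result. The documents support none of these. They do not show which source is correct, they give neither a t_max distribution nor the spread around 3,900, and they contain no rule linking dose to the range.

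What the objection does not do is make the pairing sound. The range has no stated dose, it is not reconciled with 4.5.1, and it describes C_max while the sample is a fixed-time value that can equal C_max or fall below it.

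**Conclusion.** The point holds as a limited one, worth correcting. On the plan's own figures, comparing a 2-hour sample with a C_max-based range tends to understate exposure. The 4.5.1 peak lies 22% below the floor as reported and about 38% below at the study dose. Across the t_max range in 4.8.1, the 2-hour value runs from about 16% to 100% of C_max, and the floor is met across the cited C_max range only when the peak falls near 2 h.

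The 38% assumes dose proportionality and a serum-to-plasma ratio near 1. The percentages of C_max depend on the assumed curve. How many patients would be affected cannot be worked out from the documents. The effect is confined to a secondary PK endpoint and discretionary dosing in the capecitabine patients; the co-primary endpoints and sample size are untouched.

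Separately, section 9.4.6 says "A validated assay will be used to measure plasma drug concentration", whereas 4.8.1 and Appendix E specify serum. That is a clerical slip and carries no weight in this conclusion.

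**What to change.** In 4.8.1, report the value as the 2-hour post-dose concentration (C2h) in place of the peak. State that 5,000-10,000 ng/mL will not be used to classify exposure or to inform dosing under 4.1(8) unless it is replaced by a 2-hour serum reference for 1000 mg/m², with its source dose and matrix given and reconciled with 4.5.1. Change plasma to serum in 9.4.6 as a clerical correction.

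The cost is wording only, with no extra samples or visits. The downside is that the plan has no capecitabine target range until such a reference is cited.

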4.8.2 Imatinib

Imatinib is an oral tyroskine kinase inhibitor (TKI) used for the treatment of gastrointestinal stromal tumor (GIST), chronic myeloid leukemia (CML) and Philadelphia positive (Ph+) acute lymphocytic leukemia (ALL). Imatinib is administrated as imatinib mesylate, which is rapidly converted by non specific esterases into imatinib. Imatinib undergoes CYP-mediated metabolism with CYP3A4 and CYP3A5 being the major enzymes involved. N-demethylimatinib is the predominant metabolite and it was observed with pharmacological activity similar to that for the parent drug [74]. Imatinib has a $t_{1/2}$ of approximately 20 hours, and a t_{max} of 2-4 hours with a C_{max} around 3,200 ng/mL.

Dosage: Imatinib 400 mg daily. A dose increase up to 800 mg daily (given as 400 mg twice daily) may be considered by the investigator, as clinically indicated, in patients showing clear signs or symptoms of disease progression at a lower dose and in the absence of severe adverse drug reactions.

Sampling: Trough levels of imatinib will be measured on day 2 at 24 ± 3 hours post-dose [67, 75].

Sample Handling: Peripheral blood will be collected in a tube and will be allowed to clot for 30-60 min following by centrifugation at 3000 rpm, 4°C, for 10 min.

Sample Storage: Serum samples will be stored at -80°C.

Extraction: Imatinib will be extracted from the serum samples using the above mentioned protein precipitation extraction procedure. Minimum volume of blood sample considering duplicates for TDM (and PK) studies should be no less than 300 μ L (120 μ L is needed for one extraction).

Quantification: Concentration of imatinib will be measured by a New York State Department of Health (and thereby CLIA-) approved LC-MS/MS assay developed for the simultaneous quantification of OncoTreat-prioritized drugs. The method is based on an existing New York State DOH-approved assay for imatinib developed by CPTL for its clinical services, with only minor modifications.

Target Range: The target range for imatinib trough levels will be the same as currently used clinically and is 1,000 - 3,200 ng/mL in serum.

4.8.3 **Ruxolitinib**

Ruxolitinib inhibits the Janus-associated kinase-1 and -2 (JAK 1/2) enzymes and is FDAapproved for the treatment of myelofibrosis, polycythemia vera, and graft-versus-host disease. CYP3A4 is the major enzyme mediating hydroxylation of ruxolitinib. Different formulations are available for this drug from 5 mg to 20 mg tablets. Ruxolitinib has a $t_{1/2}$ of 2.6 - 5 hours, a t_{max} of 1 - 3 hours, and reaches a C_{max} of 60 or 570 ng/mL for doses of 5 mg or 50 mg, respectively [76, 77].

Dosage: Ruxolitinib 15 mg BID given orally twice per day. A dose increase up to 25 mg BID may be considered by the investigator, as clinically indicated, in patients showing clear signs or symptoms of disease progression at a lower dose and in the absence of severe adverse drug reactions.

Sampling: Trough levels of ruxolitinib will be measured on day 2 at 24 ± 3 hours post-dose. On day 2, the trough level is expected at a concentration around 3 ng/mL [77].

Sample Handing: Peripheral blood will be collected in a tube and will be allowed to clot for 30 - 60 min following by centrifugation at 3000 rpm, 4°C, for 10 min.

Extraction: Ruxolitinib will be extracted from the serum samples using the above mentioned protein precipitation extraction procedure. Minimum volume of blood sample considering duplicates for TDM (and PK) studies should be no less than 300 μ L (120 μ L is needed for one extraction).

Quantification: Concentration of ruxolitinib will be measured by a New York State Department of Health (and thereby CLIA-) approved LC-MS/MS assay developed for the simultaneous quantification of OncoTreat-prioritized drugs. The method is based on an existing New York State DOH-approved assay for imatinib developed by CPTL for its clinical services, with only minor modifications.

Target Range: The target range for ruxolitinib trough concentration in serum will be 15 - 60 ng/mL.

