(7) Subjects who are initiated on an OncoTreat-prioritized drug will have an optional ontreatment 'pharmacodynamic' biopsy performed within one month of initiating treatment and within 24 hours of the most recent dose. This biopsy will be performed as 'proof-of-principle' that OncoTreat prioritized drugs result in collapse of the master regulator architecture (also known as master regulator signature) of the tumor, *in vivo*.

(8) Peripheral blood will be drawn for routine laboratory testing, tumor markers (CA 19-9), and research testing for biomarker analysis. Pharmacology measurements will also be drawn weekly during Cycle 1 of treatment. [name], the Director of Clinical Pharmacology and Toxicology Laboratory (CPTL), will make available CLIA assays for every FDA-approved drug and will provide assays for any investigational agents that match to the subjects in the study. Pharmacokinetic (PK) results and toxicity may be used by the treating physician, after discussion with the Investigator, to modify dosing schedule as appropriate.

(9) Adverse events will be monitored and recorded (Section 8).

(10) Subjects will undergo routine standard-of-care radiographic assessments (CT preferred) at baseline and every 8 weeks with response measured per RECIST v1.1 (Section 10).

(11) Subjects will continue on study treatment until radiographic disease progression or death, intolerance to the study drug, or withdrawal of consent. Patients will not be permitted to continue study treatment after disease progression per RECIST v1.1 criteria (Section 10).

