4.5.2 Imatinib

Pharmacokinetic studies of imatinib in healthy volunteers and patients with CML, GIST, and other cancers show that orally administered imatinib is well-absorbed, and has an absolute bioavailability of 98% irrespective of oral dosage form or dosage strength [49]. Food has no relevant impact on the rate or extent of bioavailability. The terminal elimination half-life is approximately 18 hours. Imatinib plasma concentrations predictably increase by 2- to 3-fold when reaching steady state with 400 mg once daily administration.

Imatinib is approximately 95% bound to human plasma proteins, mainly albumin and α_1 -acid glycoprotein [50]. The drug is eliminated predominantly via the bile in the form of metabolites. The fecal to urinary excretion ratio is approximately 5:1 [51].

Imatinib is metabolized in the liver mainly by the cytochrome P450 (CYP) 3A4 or CYP3A5 and can competitively inhibit the metabolism of drugs that are CYP3A4 or CYP3A5 substrates. Interactions may occur between imatinib and inhibitors or induces of these enzymes, leading to changes in the plasma concentration of imatinib as well as coadministered drugs. Major induces of CYP3A4 and CYP3A5 activity may increase metabolism and decrease exposure to imatinib (e.g. carbamazepine, dexamethasone, barbituates, phenytoin, rifampin, and St. John's Wort). Concomintant CYP3A4 and CYP3A5 inhibitors should be administered with caution (e.g. cimetidine, erythromycin, clarithromycin, ketoconazole, itraconazole, cyclosporine, grapefruit juice).

Hepatic and renal dysfunction, and the presence of liver metastases, may result in more variable and increased exposure to the drug, although typically not necessitating dosage adjustment.

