In patients with advanced or metastatic GIST, who were treated with imatinib 400 mg once daily, mean plasma tough level (C_{trough}) was higher in patients who responded to treatment. A target threshold of >1,100 ng/mL has been defined [63-65]. These results are similar to results previously found in patients with CML [66-68].

We will use therapeutic drug monitoring (TDM) in this clinical trial with the hope of establishing exposure-response relationship.

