- k. An optional on-treatment tumor biopsy is requested and will be performed within one month of initiation of an OncoTreat-prioritized drug (28 days ±7 days). The biopsy is to be done within 24 hours of administration of the most recent dose. An optional end-of-treatment tumor biopsy is also requested (±7 days of completing OncoTreat-prioritized drug).
- 1. Collect on Cycle 1 Day 1 and Cycle 2 Day 1 (prior to study treatment administration).
- m. Screening ECOG performance status should be performed within 3 days prior to the first dose of the OncoTreat-prioritized agent.
- n. Serum CA 19-9 will be collected prior to dose administration on Day 1 of each cycle.
- o. On days with PK assessments, patients should not eat breakfast or take the OncoTreat-prioritized agent at home. Upon arrival to the clinic, whole blood will be obtained premorning dose for imatinib and ruxolitinib. Patients will then take the medication as instructed by the clinic staff. For capecitabine, patients will take the medication as instructed by the clinic staff then will have whole blood obtained for PK analysis. See Section 4.8 for details.

Capecitabine: cycle 1 day, cycle 1 day 8

Imatinib: cycle 1 day 2 (24 hours \pm 3 hours after cycle 1 day 1 dose administration)

Ruxolitinib: cycle 1 day 2

p. Baseline transthoracic echocardiogram (TTE) is required for all subjects on the imatinib-treated arm.

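### The imatinib trough that Section 4.8.2 schedules follows the first dose, yet it is set against a clinical range that appears to describe steady state, so many adequately exposed subjects may be classed as below target

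*Combined protocol and SAP*

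**What the plan says.** **Sample.** Section 4.8.2: "Trough levels of imatinib will be measured on day 2 at 24 ± 3 hours post-dose". Footnote o of Table 6 (Section 9.1) places it on cycle 1 day 2, 24 ± 3 "hours after cycle 1 day 1 dose administration", and adds that "whole blood will be obtained premorning dose for imatinib and ruxolitinib". Neither place lists another imatinib sample. Section 9.4.6 confines PK sampling to Cycle 1 and refers to Section 4.8 for timing, as does the imatinib calendar (Table 8).

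**Comparator.** Section 4.8.2: "The target range for imatinib trough levels will be the same as currently used clinically and is 1,000 - 3,200 ng/mL in serum". Section 4.6.2, discussing GIST patients treated with 400 mg once daily, says: "A target threshold of >1,100 ng/mL has been defined".

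**Accumulation.** Section 4.5.2: "Imatinib plasma concentrations predictably increase by 2- to 3-fold when reaching steady state with 400 mg once daily administration". It gives a half-life of about 18 hours; Section 4.8.2 gives about 20 hours.

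**Frequency and use.** Section 4.1, item (8): "Pharmacology measurements will also be drawn weekly during Cycle 1 of treatment". The same item says that "Pharmacokinetic (PK) results and toxicity may be used by the treating physician", after discussion with the investigator, to alter the dosing schedule. Section 4.6.2 hopes that drug monitoring will establish an exposure-response relationship. Section 2.2.2 lists concentrations, and their relation to other endpoints, as secondary endpoints.

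**The concern.** The sample and its yardstick seem to describe different states. A level 24 hours after one dose has not yet accumulated, whereas a range taken from patients on continuing daily treatment has. Reading one against the other biases the classification downward at the lower limit. It also makes the upper limit too lenient, because a first-dose value well inside the range may lead to a steady-state trough above it.

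Two uses are exposed. One is the relation between exposure and outcome: a first-dose level does not capture how far each subject accumulates. Section 4.5.2 itself warns that organ dysfunction and liver metastases may make exposure higher and more variable. The other is drug monitoring, since Section 4.1 allows PK results to inform dosing. If only the day-2 sample is drawn, the steady-state value cannot be recovered later, because PK sampling ends with Cycle 1.

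**Working it through.** **Inputs.** Dosing interval 24 h (400 mg once daily, Section 4.3.2); half-life 18 h (4.5.2) or 20 h (4.8.2); stated accumulation 2- to 3-fold (4.5.2); range 1,000-3,200 ng/mL (4.8.2), width 2,200; threshold 1,100 ng/mL (4.6.2); Cmax about 3,200 ng/mL at 2-4 h (4.8.2).

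**Assumptions.** One-compartment linear kinetics with unbroken dosing at a constant dose. The stated accumulation, which Section 4.5.2 gives for plasma concentrations generally, is applied to troughs.

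**Step 1: the plan's own accumulation figure.** R = 1 / (1 − 2^(−24/t½)).
- t½ = 18 h: 1 / (1 − 0.397) = 1.66
- t½ = 20 h: 1 / (1 − 0.435) = 1.77

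The stated 2- to 3-fold is not reproduced. R = 2 needs a half-life of 24 h, and R = 3 needs about 41 h. Both sets of values are carried forward.

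**Step 2: from steady state to day 2.** Day-2 level = steady-state trough / R. The trough needed to read 1,000 on day 2 is 1,000 × R. The misread band as a share of range width is (1,000 × R − 1,000) / 2,200. The day-2 level matching the upper limit is 3,200 / R.

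| R | Steady-state trough needed to read 1,000 | Misread band, share of range width | Day-2 reading at a 1,100 trough | Day-2 reading at a 3,200 trough |
|---|---|---|---|---|
| 1.66 (18 h) | 1,658 | 30% | 663 | 1,930 |
| 1.77 (20 h) | 1,771 | 35% | 621 | 1,807 |
| 2 (stated) | 2,000 | 45% | 550 | 1,600 |
| 3 (stated) | 3,000 | 91% | 367 | 1,067 |

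The last column gives the upward error. A day-2 reading between that figure and 3,200 counts as in range, although the implied steady-state trough exceeds 3,200.

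**Step 3: sampling window.** Sampling at 21 or 27 h multiplies the reading by 1.12 or 0.89 (18 h half-life), or by 1.11 or 0.90 (20 h). This is smaller than the accumulation effect.

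**Step 4: check against the stated Cmax.** Level at 24 h = 3,200 × 2^(−(24 − tmax)/t½), which is 1,372-1,600 ng/mL over the stated tmax and half-lives.
- If 3,200 is a steady-state Cmax, 1,372-1,600 is the steady-state trough, and day 2 reads 457 (1,372/3) to 904 (1,600/1.77). That is below 1,000 in every case.
- If 3,200 is a first-dose Cmax, day 2 reads 1,372-1,600, which is in range. At 2- to 3-fold accumulation the later trough is then about 2,740 (1,372 × 2) to 4,800 (1,600 × 3), which can exceed the upper limit.

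**Step 5: would a week-3 sample be at steady state?** Fourteen daily doses span 336 h. That is 336/20 = 16.8 half-lives at 20 h, and 336/41 = 8.2 half-lives even at the value needed for 3-fold accumulation, where the fraction of steady state is 1 − 2^(−8.2), above 99%.

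**The case against.** Several points on the other side are fair.

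- **The range is not labelled steady state.** Section 4.8.2 says only that it is in current clinical use. Steady state is an inference from that and from the treated GIST patients in Section 4.6.2. It is a strong inference, but it remains one.
- **A reader might infer that adequately exposed subjects will read low as a rule.** The documents do not support that. Subjects with high enough steady-state troughs read in range under every R, and the Cmax is not identified as first-dose or steady-state. On the first-dose reading, a typical day-2 level is within range.
- **A reader might take 45-91% as the size of the problem, or as a share of patients.** It is neither. The plan's half-lives give 30-35%, and all these figures are shares of the range's width. No distribution of troughs is given, so the share of patients is unknown.
- **A reader might say that no other PK sample is planned.** Section 4.1 says weekly draws in Cycle 1. With half-lives of 18-20 h, draws from day 8 would be essentially at steady state. This part stands as a conflict to resolve. The detailed sections favour one sample: Section 9.4.6 and Table 8 both defer to Section 4.8, which lists only day 2.
- **The consequences are limited.** No primary endpoint uses the value. The secondary endpoint is concentration, not the proportion in range. No imatinib dose rule in Sections 4.3.2 or 4.9.3 acts on the range, and the use of PK in Section 4.1 is permissive. Section 12 plans on 9 treated subjects as the minimum expected, and Section 2.2.2 expects very few per drug, so little exposure-response information would emerge at any sampling time.

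These points limit the weight of the finding. They do not explain why a first-dose level is set against this range without adjustment.

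**Conclusion.** The mismatch is real, and its direction follows from the plan's own statement that concentrations rise to steady state. Its size is uncertain because the stated accumulation and the stated half-lives disagree. A subject needs a steady-state trough of about 1,660-1,770 ng/mL on the half-lives, or 2,000-3,000 ng/mL on the stated accumulation, before day 2 reads 1,000. Subjects between 1,000 and that figure would be misclassified as low. Some in-range readings would conceal a trough above the upper limit.

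This rests on linear accumulation and on the inferred steady-state origin of the range. It should be fixed, but it concerns secondary and exploratory measures in few subjects and does not threaten the trial's main conclusions.

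**What to change.** Take the imatinib trough that is compared with 1,000-3,200 ng/mL as a pre-dose sample at the week-3 visit in Table 8. That visit already includes blood tests and falls within the 28-day Cycle 1. Amend Section 4.8.2 and footnote o to match. If the day-2 sample is kept, report it as a first-dose 24-hour concentration and not against this range.

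Reconcile:
- sampling frequency: Section 4.1 item (8) against Section 4.8.2, footnote o and Section 9.4.6;
- half-life and accumulation: Section 4.5.2 against Section 4.8.2, and the 2- to 3-fold figure against both half-lives;
- the lower limit: 1,100 ng/mL in Section 4.6.2 against 1,000 ng/mL in Section 4.8.2.

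This review does not choose the threshold or any dosing rule. The plan should also say whether the range and the Cmax refer to steady state.

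**Cost.** A short amendment and some added work at week 3: breakfast and the morning dose must be held until the draw, dose and sample times recorded, and PK serum processed. Subjects who stop before week 3 would have no steady-state value.
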